**STATISTICAL ANALYSIS:** For analysis of aims 1, 2 and 3, linear mixed effects models will be used to compare change in UEFM (primary endpoint), WMFT rate, functional ability, grip strength, SIS, IHI, functional connectivity, and ipsilateral MEP area from baseline to end-of-treatment (and 3-month follow-up) between groups. Models will account for spasticity, baseline wrist extension (none;  $\leq 10^\circ$ ;  $> 10^\circ$ ), lesion size/location, time post-stroke, side of paresis, biologic variables (e.g., sex) and handedness. Bivariate (Pearson's) correlation will be used to explore relationships between change in function and change in IHI, functional connectivity and ipsilateral MEP area. Chi-square or Fisher's Exact test will help compare the frequency of responders (those achieving  $\geq 5.2$ -point UEFM gain [84]) and patients showing restoration of ipsilesional MEPs (MEP+) between groups. For aim 4, regression models will capture the influence of baseline  $FA_{\text{Asymmetry}}$  upon improvements associated with facilitation of cPMd vs. iM1, and separately the influence of baseline UEFM and wrist extension.

Additional data analysis will be conducted using quantum machine learning (QML) to develop a classification model for assessing the functional capacity of stroke patients to use the affected upper extremity. We will utilize behavioral outcome measures signifying the functional capacity collected during this study. The ultimate goal of this analysis is to discern variations in functional capacity among individuals affected by stroke for tailoring rehabilitation interventions to each patient's specific needs.

**Potential Pitfalls and Alternative Solutions:** *If not all patients can elicit ipsilateral MEPs in the paretic muscle*, we will compare groups upon the frequency of evidence of these MEPs after treatment (Chi-square/Fisher's Exact) [4, 52, 57, 58, 60-73]. *If effects of cPMD facilitation are weak*, we will perform sub-group analyses based on baseline wrist extension to determine which category of patients shows the best response. We will also determine what level of baseline FAAsymmetry, connectivity, impairment (UEFM) predicts response vs. non-response (based on attainment of 5.2-point UEFM gain [84]). *Anticipating that cPMD facilitation may have effects on bilateral control*, we will adopt bimanual test used in our recent study [159].

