## APPROACH

**Study Design and Criteria:** In a pilot, randomized-controlled, single-blind study, a target of 24 patients will be assigned to either receive facilitation of cPMd or facilitation of iM1 (conventional approach), delivered daily in conjunction with rehabilitation for 2 days/wk for 6 wks. They will be assigned to treatment groups using a stratified randomization scheme to minimize group imbalances on 4 key patient characteristics: (1) time post-stroke (<2 yrs vs.  $\geq$ 2 yrs), (2) cortical vs. subcortical stroke, (3) presence of active wrist extension vs. no wrist extension, and (4) paretic side (dominant vs. non-dominant). Assessments will be completed at baseline and at the end of treatment after 6 wks, except assessments for Aim 1 that will also be completed at screening and at 3-month follow-up visit (Table 1). Ten age matched healthy controls, fifteen age matched mild, and up to 5 moderately impaired participants (who will undergo rTMS and CCFES based-therapy) will also be enrolled to record comparative neural indices. The goal will be to establish age-based norms for healthy, mild, moderate, and severe neurophysiologic metrics related to EDC, FDI, Biceps, and Triceps muscles.

Table 1: Schedule of Assessments		Screening & Eligibility	Baseline (0 weeks)	End-of-Treatment (6 weeks)	Follow-up (3 months)
History, Physical & Neurological Examination		X			
Eligibility testing: Inability to elicit MEPs (TMS), i.e., MEP-		X			
Aim 1	Impairment (UEFM)			X	X
	Functional Ability (WMFT)		X	X	X
	Distal movement (Grasp/Grip Strength)		X	X	X
	Patient-perceived Disability (SIS-16)		X	X	X
Aim 2	IHI imposed on iM1 (TMS)		X	X	
	Inter-hemispheric connectivity (resting state fMRI)		X	X	
Aim 3	Uncrossed pathways or Ipsilateral MEPs (TMS)		X	X	
	Ipsilesional corticospinal damage (DTI)		X		
Aim 4					

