### Sample size Estimation and Power

**Analysis:** Table 2 shows sample size estimations based on two-sample t conducted across difference scores between groups. We expect to enroll 22 subjects but in accounting for ~10% attrition, a total of 24 subjects will be enrolled.

Table 2: Sample Size Estimation

Aim	Metric	cPMD vs. iM1		Alpha	80% 85% 90% 95%			
		UEFM	IHI		14	16	18	22
Aim 1		9±1.41 vs. 4.3±3.56	-9.25±5.89 vs. 6±14.05	0.05	14	16	18	22
Aim 2				0.05	20	22	26	30
Aim 3	Ipsilateral MEP	311.63±29.96 vs. 255.75±93.29		0.05	22	24	38	46
Aim 4	DTI $\alpha$ UEFM	15% diff. in slopes		0.05	18	20	23	28

**IMPACT:** While greater damage produces greater impairment following stroke, it also generates a widespread plastic response involving the intact cortices in the contralesional hemisphere. Although this response may not be sufficient to support complete recovery, it is likely to support more recovery than what is otherwise possible to achieve [4]. Demonstrating that facilitating these intact areas can lead to restoration of paretic-limb function in patients who fail to benefit from any therapies on account of extensive damage will carry tremendous clinical impact, provide the impetus to develop targeted therapies and depart from conventional beliefs that have always disparaged the potential offered by the intact hemisphere.

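### Stratifying 24 patients on four binary factors gives, if fully crossed, 16 cells averaging 1.5 patients; this serves the balance aim poorly at usual block sizes, and the SAP comparison does not adjust for the factors

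*Protocol*

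**What the plan says.** The protocol (Approach, Study Design and Criteria) states that "a target of 24 patients will be assigned to either receive facilitation of cPMd or facilitation of iM1". The method is a "stratified randomization scheme to minimize group imbalances on 4 key patient characteristics": time since stroke (cut at 2 years), cortical or subcortical lesion, active wrist extension present or absent, and paretic side dominant or not. It does not give a block size or an allocation ratio, does not say whether the four factors are crossed, and does not say whether a dynamic method is used.

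On sample size the protocol says: "We expect to enroll 22 subjects but in accounting for ~10% attrition, a total of 24 subjects will be enrolled".

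The two documents differ on adjustment. The protocol's Statistical Analysis section plans linear mixed models that account for wrist extension, lesion size and location, time since stroke, side of paresis and handedness, among other covariates; together these cover the four stratification factors. The SAP compares change scores between groups with independent t-tests or Wilcoxon rank sum tests and names no covariates. It is dated 10/23/24 and written in the past tense.

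**The concern.** Stratified permuted blocks balance the arms only where blocks are completed. With four binary factors and 24 patients, most cells would hold too few patients to complete a block. Each unfinished block leaves a small random surplus in one arm, and across many cells these surpluses add up, both in the arm totals and on each factor. The scheme can then fall well short of its stated purpose, even though another method could meet that purpose at this sample size.

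The protocol regards these factors as important: it calls them key characteristics, and its Stimulation section describes wrist extension as a key predictor of recovery. The SAP's unadjusted comparison would carry any remaining imbalance on them into the estimated group difference.

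**Working it through.** **Inputs from the documents.** N = 24 randomised, 22 evaluable; four factors with two levels each; UEFM change "9±1.41 vs. 4.3±3.56"; alpha 0.05; "two-sample t conducted across difference scores between groups".

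**Assumptions.** 1:1 allocation, fully crossed strata, and 50% prevalence for each factor (range checked: three factors at 30%, one at 50%). None of these is stated.

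**1. The plan's own figure.** The difference is 9 − 4.3 = 4.7 points. A two-sided two-sample t-test with unequal variances gives totals of 14, 16, 18 and 22 at 80, 85, 90 and 95% power, which matches the UEFM row of Table 2. Attrition: 22 × 1.1 = 24.2 and 22 / 0.9 = 24.4, close to 24. The sample size is therefore not in question.

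**2. Cells.** 2⁴ = 16; 24 / 16 = 1.5 patients per cell (22 / 16 = 1.4 evaluable).

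**3. Occupancy, Binomial(24, 1/16) per cell.**
- Empty: 16 × (15/16)²⁴ = 16 × 0.2125 = 3.4 cells, so 12.6 are occupied.
- One patient: 16 × 24 × (1/16) × (15/16)²³ = 5.4 cells.
- Four or more: 16 × 0.0595 = 0.95 cells.

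So only about one cell in 16 would complete a block of 4. With three factors at 30%, about 5.2 cells are empty and 4.6 hold one patient.

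**4. Balance by simulation** (several thousand trials per scheme). The factor gap is the largest difference between arms, over the four factors, in the proportion of patients at a given level. Minimisation sums the arm difference over the new patient's four factor levels and assigns the lagging arm with probability 0.8 or 0.9.

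| Scheme | 14:10 split or worse | Gap of 25 points or more on some factor |
|---|---|---|
| Simple randomisation | about 55% | about 69% |
| 16 strata, blocks of 2 | about 27% | about 19% |
| 16 strata, blocks of 4 | about 40% | about 43% |
| 16 strata, blocks of 6 | about 46% | about 55% |
| Minimisation, 0.8 coin | about 4% | about 20% |
| Minimisation, 0.9 coin | about 1% | about 7% |

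Repeated runs differ by one or two points for the blocked schemes, and range from 18% to 24% for the factor gap with the 0.8 coin.

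**5. Sensitivity to prevalence.** With three factors at 30% and one at 50%, a 14:10 or worse split occurs in about 23%, 36% and 42% (blocks of 2, 4 and 6), against about 4% with the 0.8 coin. A 25-point gap occurs in about 13%, 32% and 42%, against 18 to 23% with the 0.8 coin and 63% with simple randomisation. The pattern is the same, except that blocks of 2 then do somewhat better than the 0.8 coin on the factor gap.

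**6. Cost of unequal arms.** Variance ratio of 14:10 to 12:12: (1/14 + 1/10) / (1/12 + 1/12) = 0.1714 / 0.1667 = 1.029. Variance rises by 2.9% and the standard error by 1.4%.

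**The case against.** The strongest objection is that the text does not describe the criticised design. The protocol never mentions 16 strata or a block size, and its wording does not exclude minimisation. This stands: full crossing is the plain reading, not a documented fact. If a dynamic method was used, what remains is that the method was not specified.

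Three stronger readings are tempting, and the documents support none of them.

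- *The scheme cannot deliver balance.* Crossed strata reduce the chance of a 25-point gap at every block size tried, from about 69% with simple randomisation to between 19% and 55%. Blocks of 2 do about as well on this measure as minimisation with a 0.8 coin.
- *Imbalance could be as large as the effect sought.* The documents give no association between any of these factors and UEFM change. With a 25-point gap, one factor would have to shift UEFM change by 4.7 / 0.25 = 18.8 points to produce a 4.7-point bias, about twice the 9-point gain expected in the better arm.
- *Balance by design is the only protection.* This describes the SAP comparison but not the protocol, whose models were to account for these factors, though with many covariates for 24 patients.

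It is also fair that unequal arms cost little precision, that this is a pilot, and that the past-tense SAP suggests allocation is finished. The advantage of blocks of 2 has a price: once the first assignment of a pair is known, the second is determined, which matters in a single-blind trial. They also leave the 27% chance of a 14:10 or worse split.

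**Conclusion.** The point holds in a limited form. If the four factors are fully crossed, the scheme improves on simple randomisation but serves its stated aim poorly at block sizes of 4 or 6: a 25-point gap on some factor in about 43% or 55% of trials, against about 20% or 7% with minimisation using a 0.8 or 0.9 coin. Arm sizes of 14:10 or worse occur in about 27 to 46% of trials, against about 4% with the 0.8 coin, although the loss of precision is small. Blocks of 2 bring factor balance level with the 0.8 coin only by making every second assignment in a stratum predictable.

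The consequence is residual chance imbalance that the SAP's unadjusted comparison leaves in place, although the protocol planned to account for it. How much this would move the UEFM difference cannot be computed from the documents. The figures rest on full crossing, 1:1 allocation and the assumed prevalences. This is a cheap improvement and does not invalidate the trial.

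**What to change.** **Allocation, for patients not yet randomised or a successor trial.** Replace crossed strata with minimisation on the margins of the same four factors, with a random element of 0.8 to 0.9. State the algorithm and the allocation ratio. The cost is a small allocation program in place of lists, and slightly more predictable allocation, which the random element limits. Stratifying on one factor alone is not an adequate substitute unless the others are adjusted for in the analysis: it leaves a 25-point gap on some factor in about 64% of trials.

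**Analysis, for patients already allocated.** State which scheme and block size were used, and tabulate arm sizes and the four factors by arm. Adjust the between-group change-score comparison for the stratification factors, at least wrist extension, as the protocol's Statistical Analysis section planned, and report it beside the SAP's unadjusted comparison. This needs no new data. With 24 patients the covariate list should be kept short, which is why wrist extension comes first.

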**AIM 4: Explore how ipsilesional corticospinal damage influences response to cPMd facilitation.** At baseline, damage to ipsilesional corticospinal pathways will be indexed using DTI. DTI enables the investigation of structural integrity and orientation of pathways *in vivo* through the estimation of magnitude and directionality of water diffusion [69, 145-149]. DTI metrics can help quantitate damage even when patients show no response to TMS due to extensive damage (MEP-) (Fig. 4B) [3, 47, 69]. High angular resolution diffusion weighted images will be acquired and analyzed using steps outlined in our work with [name] [34, 47, 91, 150-154]. Ipsilesional and contralesional corticospinal tracts will be reconstructed using probabilistic tractography [47, 91, 153, 155]. FA, a unit-less measure of white matter integrity, will be calculated [156, 157].  $FA_{\text{Asymmetry}}$  given by  $FA_{\text{Contralesional}} - FA_{\text{Ipsilesional}}/FA_{\text{Contralesional}} + FA_{\text{Ipsilesional}}$ , will be used to express integrity of ipsilesional vs. contralesional tracts. Higher values of  $FA_{\text{Asymmetry}}$  indicate severe damage. Stroke neurologist, [name], will identify lesion location (posterior limb of internal capsule (PLIC) or non-PLIC) and volume ( $\text{cm}^3$ ) [158].

**Expected outcomes and interpretations:** Based on our AHA study, we expect that improvements associated with facilitation of cPMd will vary as a function of baseline corticospinal damage [3]. This would allow identification of a threshold level of damage, beyond which patients fail to show criterion-level improvement (5.2-point gain [84]) on UEFM, necessary for responder stratification for this new approach involving facilitation of intact areas.

**Figure 4.** (A) Group rsfMRI data from moderately/severely-impaired patients (n=9) reveals areas in ipsilesional M1 and sensory cortices (S1) (MNI: X: 49 Y: 29 Z: 48) that show an increase in functional connectivity with cPMd (MNI: 26, -6, 53) (peak t-value= 3.25) following rehabilitation. (B) Examples from our work demonstrating the feasibility of successfully generating FA maps (top) and reconstructing corticospinal tracts (bottom) in patients with severe (left panel) and mild damage (right panel).

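### The FA asymmetry formula for Aim 4 is printed without brackets, and read literally it does not measure asymmetry

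*Protocol*

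**What the plan says.** The protocol's Aim 4 section (under Approach) indexes corticospinal damage at baseline with diffusion imaging. It gives the asymmetry index as "FA_{\text{Contralesional}} - FA_{\text{Ipsilesional}}/FA_{\text{Contralesional}} + FA_{\text{Ipsilesional", states that the index "will be used to express integrity of ipsilesional vs. contralesional tracts", and adds that higher values "indicate severe damage".

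The index has two uses in the protocol's Statistical Analysis section:

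- **Regression.** "For aim 4, regression models will capture the influence of baseline" FA asymmetry "upon improvements associated with facilitation of cPMd vs. iM1, and separately the influence of baseline UEFM and wrist extension".
- **Response threshold.** Under Potential Pitfalls and Alternative Solutions: "We will also determine what level of baseline FA Asymmetry , connectivity, impairment (UEFM) predicts response vs. non-response", where response is a 5.2-point UEFM gain. The Aim 4 section also looks for a level of damage past which patients do not reach that gain.

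FA asymmetry is the only measure of corticospinal damage named as a regressor for Aim 4. The Aim 4 section also says that a neurologist "will identify lesion location (posterior limb of internal capsule (PLIC) or non-PLIC) and volume", but no Aim 4 analysis names these two measures. Lesion size and location appear only as covariates in the models for Aims 1 to 3. No bracketed version of the formula appears elsewhere in the protocol, and the SAP mentions neither FA nor DTI.

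**The concern.** Division binds before addition and subtraction, so the printed rule divides only ipsilesional by contralesional FA and then adds and subtracts the remaining terms. The result depends on the absolute FA of the intact tract as well as on the relative loss on the lesioned side. Two patients with the same proportional loss can then score differently, and a less damaged patient can score higher than a more damaged one.

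If the rule were coded as printed, the Aim 4 regression would relate treatment response to a mixture of damage and contralesional FA. A response threshold taken from it would also mean something different from a threshold on the bracketed index, so another group could not apply it reliably.

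**Working it through.** **Inputs.** The formula, its purpose and its direction come from the protocol's Aim 4 section. There FA is described only as unit-less ("FA, a unit-less measure of white matter integrity, will be calculated"). The documents give no FA or FA asymmetry value, so there is no figure to reproduce, and every FA value below is an assumption.

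**Two forms.**
- Printed: W = C - I/C + I
- Bracketed: B = (C - I)/(C + I)

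**Step 1: symmetric tracts (C = I = x).** W = x - 1 + x = 2x - 1, and B = 0.
- x = 0.40: W = -0.20
- x = 0.50: W = 0
- x = 0.60: W = +0.20

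W is zero only at x = 0.50, and B is zero throughout.

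**Step 2: equal relative damage.** Put I = rC. Then B = (1 - r)/(1 + r), which depends only on r, while W = C(1 + r) - r, which also changes with C. With r = 0.5:
- (0.40, 0.20): W = 0.40 - 0.50 + 0.20 = 0.10; B = 0.20/0.60 = 0.333
- (0.60, 0.30): W = 0.60 - 0.50 + 0.30 = 0.40; B = 0.30/0.90 = 0.333

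A cut-off of, say, 0.20 on W would separate these two patients although their proportional loss is the same.

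**Step 3: order reversal between two damaged patients.**
- (0.55, 0.40): W = 0.55 - 0.727 + 0.40 = 0.223; B = 0.15/0.95 = 0.158
- (0.45, 0.25): W = 0.45 - 0.556 + 0.25 = 0.144; B = 0.20/0.70 = 0.286

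The second patient is the more damaged on B but scores lower on W.

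**Step 4: direction at fixed C.** The slope of W in I is 1 - 1/C, which is negative for C < 1. For a given contralesional FA, W therefore still rises as ipsilesional FA falls. The reversals come from differences in C between patients.

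**Step 5: how often the order reverses.** Simulated patients (200,000 draws, 100,000 pairs), with C uniform on the range shown and I/C uniform on 0.5 to 1:

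| Range of C | Pairs in opposite order | Spearman correlation of W and B |
|---|---|---|
| 0.54–0.56 | 5% | 0.99 |
| 0.50–0.60 | 21% | 0.79 |
| 0.45–0.65 | 32% | 0.52 |
| 0.40–0.70 | 37% | 0.37 |

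With C normal (mean 0.55) and the same range of I/C, the shares are 15%, 21% and 29% for an SD of 0.02, 0.03 and 0.05. A bivariate normal model (mean C 0.50, SD 0.02–0.05; mean I 0.36, SD 0.04–0.08; correlation 0–0.6) gives 12% to 34%, which lies within the same range.

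**The case against.** The strongest reply is that this is a typographical slip. The name of the index, its stated direction and the difference-slash-sum layout all point to (C - I)/(C + I). The protocol refers its diffusion analysis to steps in cited prior work, and nothing in the documents shows that the literal form was coded or planned. That stands, and it makes the harm conditional. It does not remove the point: the formula is a stated analysis rule, it is wrong as printed, and no other place in the documents corrects it.

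Brackets could also have been lost when the PDF was read. This cannot be fully excluded, but the ipsilateral MEP area formula under Aim 3 kept its bracketed denominator.

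A reader might infer more than the documents support:

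- **That reported Aim 4 results are wrong.** The SAP reports no FA or DTI analysis, so there is no result to judge.
- **That FA asymmetry is the sole Aim 4 predictor or the only damage information.** Baseline UEFM and wrist extension are examined separately, and lesion location and volume are collected.
- **That the printed index mainly tracks the healthy side.** At (0.50, 0.35) the slope in C is 1 + 0.35/0.50² = 2.4 and the slope in I is 1 - 1/0.50 = -1.0, but the spread matters as well. With SDs of 0.02 for C and 0.08 for I, the contributions are 2.4 × 0.02 = 0.048 and 1.0 × 0.08 = 0.080, so the ipsilesional side dominates. With SDs of 0.05 and 0.04 they are 0.120 and 0.040, and the contralesional side dominates.
- **That the trial would rank an undamaged patient as more damaged.** The treatment groups are moderately or severely impaired, and the Preliminary Approach describes the target group as having FA below 50% of normal. A symmetric, undamaged pair is therefore implausible there. The reversal in Step 3 does not need one.

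**Conclusion.** The point holds as an error in the printed definition. Taken literally, the formula gives 2C - 1 instead of 0 for symmetric tracts (zero only at FA 0.50) and scores equal relative damage differently, which contradicts the purpose the protocol gives it. These two results are algebra and need no assumed distribution.

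The practical size does rest on assumptions. If the literal form were used, about 5% to 37% of patient pairs would change order, from least to most as contralesional FA varies more. These shares assume an I/C ratio between 0.5 and 1. If the enrolled patients fall mostly below that range, as the Preliminary Approach suggests, the share could differ.

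If the code already has the brackets, no result changes. Aim 4 is exploratory, and the primary UEFM comparison and its sample size do not use this index. The correction is worth making because the protocol wants a damage threshold for selecting responders, and such a threshold needs an unambiguous definition.

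**What to change.** In the protocol's Aim 4 section, print FA asymmetry = (FA_contralesional - FA_ipsilesional)/(FA_contralesional + FA_ipsilesional). Repeat the definition in the SAP if Aim 4 is to be reported there.

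Confirm that the analysis code uses this form. A quick test is that it returns 0 for any symmetric pair and 0.333 for both (0.40, 0.20) and (0.60, 0.30). Recompute the Aim 4 regression and any response threshold only if the printed form was used.

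The cost is one line of text and a code check, with no new data.

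### The protocol's UEFM model spends about 9 covariate degrees of freedom on 22 patients; Table 2's power is for an unadjusted t-test, and the SAP drops the covariates altogether.

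*Protocol*

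**What the plan says.** In the protocol, Statistical Analysis, the primary comparison is model-based: "linear mixed effects models will be used to compare change in UEFM (primary endpoint") and the other outcomes between groups. The adjustment set follows: "Models will account for spasticity, baseline wrist extension" (in three levels), then "lesion size/location, time post-stroke, side of paresis, biologic variables (e.g., sex) and handedness". Sex is given only as an example of the biologic variables, so the list has no fixed end. The text does not say whether the covariates enter as main effects or interact with time.

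The sample size section of the protocol uses a different analysis: "Table 2 shows sample size estimations based on two-sample t conducted across difference scores between groups". The Aim 1 row assumes UEFM gains of "9±1.41 vs. 4.3±3.56" and reads "0.05 14 16 18 22": alpha, then the total N for 80, 85, 90 and 95% power. The enrolment statement is "We expect to enroll 22 subjects but in accounting for ~10% attrition, a total of 24 subjects will be enrolled". No covariate, explained variance or df allowance appears.

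The SAP describes a between-group comparison of change scores by independent t-tests or Wilcoxon rank sum tests, Holm-corrected. It contains neither a mixed model nor covariates.

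**The concern.** A power figure is informative only for the analysis that will be run. When change scores are regressed on group and patient-level covariates, each covariate costs a residual df. Unless it is balanced between the groups, it also widens the standard error of the treatment effect through chance imbalance. Repeated visits do not restore these df, because the covariates vary only between patients. With 22 patients and about 9 covariate df the cost can be large, and it is recovered only if the covariates predict UEFM change well.

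Sparse factors raise a second problem. If no patient, or only one, is left-handed or has more than 10° of wrist extension, a term may be inestimable, or may simply remove that patient from the comparison. The protocol has no rule for collapsing or dropping terms, so the final model could be chosen after seeing the data. The SAP adds a third difficulty: a reader cannot tell which between-group analysis of the primary endpoint is the planned one.

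**Working it through.** **Covariate count.** Spasticity 1, wrist extension (three levels) 2, lesion size 1, lesion location 1, time post-stroke 1, side of paresis 1, sex 1, handedness 1: total 9. Aim 4 defines lesion location and volume separately, so they count as two terms. In a change-score model the residual df are 22 − 2 − 9 = 11. Because the list is open, 7 to 12 covariate df is a reasonable range.

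**Assumptions not in the documents.** Two-sided alpha of 0.05; 1:1 allocation; 1 df for each of spasticity, lesion size, lesion location and time post-stroke.

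**Reproducing Table 2.** The difference is 9 − 4.3 = 4.7. The root-mean-square SD is √((1.41² + 3.56²)/2) = 2.708, so the standardised difference is 4.7/2.708 = 1.736. At 11 per group the standard error is √((1.41² + 3.56²)/11) = 1.155 and the noncentrality is 4.7/1.155 = 4.07. An unequal-variance (Welch) t-test needs a total N of 14, 16, 18 and 22 for 80, 85, 90 and 95% power, an exact match to the Aim 1 row. Power at N = 22 is 96.4% (97.2% with the pooled t).

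**Adding k covariates that explain nothing.** The expected standard error is multiplied by √((N − 3)/(N − 3 − k)), with N − 2 − k residual df.

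| k | SE multiplier | Noncentrality | Residual df | Power |
|---|---|---|---|---|
| 0 | 1.00 | 4.07 | 20 | 97.2% |
| 1 | √(19/18) = 1.03 | 3.96 | 19 | 96.4% |
| 5 | √(19/14) = 1.16 | 3.49 | 15 | 90.4% |
| 9 | √(19/10) = 1.38 | 2.95 | 11 | 76.7% |

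Averaging power over random covariate draws, instead of using the expected inflation, gives about 78% for k = 9. On the same basis it is 85% for 7 df and 62% for 12 df.

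**Letting the covariates explain variance.** The residual SD becomes 2.708 × √(1 − R²), where R² is the within-group variance of UEFM change that the covariates explain. For k = 9, averaged over draws:

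| R² | 0 | 0.1 | 0.2 | 0.3 | 0.4 | 0.5 |
|---|---|---|---|---|---|---|
| Power | 78% | 82% | 85% | 89% | 93% | 95-96% |

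The standard error breaks even when 1 − R² = 10/19, that is R² = 0.47.

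**Stratified randomisation.** Four binary factors make 2⁴ = 16 strata for 24 patients, or 1.5 per stratum. Blocked randomisation within these strata was simulated with two dropouts and R² = 0. It assumed 50/50 splits for the other binary factors, 10% left-handed and 10% with more than 10° of extension. Power was 81% with blocks of 4 and 83% with blocks of 2, against 79% unstratified.

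**Covariates as main effects in a group-by-time model.** In one simulated complete two-visit data set the group-by-time estimate was 4.260 with standard error 0.975, both with and without nine covariate main effects. On this reading power stays at about 97%, but the adjustment does nothing for the primary contrast.

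**Estimability.** With 10% left-handed and 10% above 10° of extension, both assumed, about 18-20% of simulated trials had a rank-deficient model.

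**The case against.** A reader might infer that power under the planned model is 77-79%. The documents do not support that as a fact. The figure needs covariates that explain nothing, little balance on any of them, and a model fitted directly to change scores. The protocol states none of these. Three of the four stratification factors (time post-stroke, wrist extension, paretic side) are also model covariates, and a group-by-time model with main effects would leave power almost untouched. This objection stands, and for that reason the result is given as a range. It does not rescue Table 2: no explained variance is given to justify a value near one half, stratification over 16 cells recovers only a few points, and readings that run from 78% to 97% show that the primary model is under-specified.

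A reader might also infer that the trial misses a 95% power target. The protocol names no target and calls the study a pilot. N = 22 falls in the 95% column only for Aim 1; in Table 2 it is the 85% column for Aim 2 and the 80% column for Aim 3. Against 80%, the worst case at 9 df is about 2 points short.

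Finally, the SAP's unadjusted tests are close to the basis of Table 2, apart from the Holm correction and the rank-test option, so the covariate cost does not reach them. That is correct. But the SAP does not explain the change of method, and it is written in the past tense with findings already reported. It therefore does not settle what the protocol planned; it leaves two incompatible analyses.

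**Conclusion.** The mismatch is real: about 9 open-ended covariate df in the UEFM model, 22 evaluable patients, and a power calculation with no covariates. Its size is conditional. Under two-sided alpha, 1:1 allocation and a change-score model, power is about 78% if the covariates explain nothing, 81-83% in that case with stratification simulated, and 82% to about 95-96% for R² of 0.1 to 0.5. It is about 97% if they are only main effects in a group-by-time model. About half the variance must be explained to break even. The 18-20% rank-deficiency rate shows that sparse levels are a plausible hazard, but it rests on assumed frequencies and is not a prediction. The conflict between the protocol and the SAP needs no assumption. This should be fixed. It does not show that the trial is underpowered.

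**What to change.** Name one primary between-group model for UEFM in both documents: treatment, baseline UEFM and at most the four randomisation factors, coded as they were randomised. State whether the outcome is change or the repeated score, and how covariates enter. Move spasticity, lesion size, sex, handedness and the remaining covariates to sensitivity analyses, with a stated rule for sparse or inestimable levels. Restate the Aim 1 power for the chosen model with its R² assumption: if no covariate is prognostic, about 96% with one covariate and about 90% with five. Because the SAP already reports findings, it should also say when the unadjusted tests were chosen and why they replaced the protocol's model.

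The cost is wording in two documents, a slightly less favourable stated power, and less adjustment for chance imbalance in the primary model. No new data are needed.
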